- Agree to assume responsibility for the proper conduct of the study at this site, including complying with current relevant versions of the US Food and Drug Administration (FDA) regulations, the International Conference on Harmonization (ICH) GCP guidelines, the Declaration of Helsinki, and all applicable rules, regulations, and federal, state, and local laws relating to the conduct of clinical studies and the protection of human subjects.
- Agree not to implement deviations from or changes to the protocol or protocol amendments without agreement from the Sponsor and prior submission to and written approval (where required) from the Institutional Review Board (IRB), except when necessary to eliminate an immediate hazard to the subjects, or for administrative aspects of the study (where permitted by all applicable regulatory requirements).
- Agree to onsite monitoring of all source documents by Alkahest, Inc. or designee and to onsite inspection of source documents by appropriate regulatory authorities, including but not limited to the FDA, local governing regulatory bodies, and IRB inspectors.

Investigator's Signature

Date

Print Name

PROTOCOL SUMMARY

Title: A Randomized, Double-Blind, Placebo-Controlled Study to Assess the Safety and Tolerability of Pulsed GRF6019 Infusions in Subjects with Severe Alzheimer's Disease

Précis: This is a randomized, double-blind, placebo-controlled study to assess the safety and tolerability of GRF6019, a [REDACTED] human plasma protein fraction, administered by intravenous (IV) infusion in subjects with severe Alzheimer's disease (AD).

The study consists of approximately 20 subjects who will be randomized in a 2:1 ratio to active GRF6019 or placebo. Treatment groups will be stratified by sex. Subjects will receive one infusion per day of active or placebo treatment for 5 consecutive days during Week 1 of the study. The total study duration for the subjects will be approximately 9 weeks.

The infusion procedure of active and placebo agents will be identical to maintain blinding. The following measures will be taken to ensure adequate allocation concealment during infusions: blinding of subjects, study coordinators, physicians, and cognitive test administrators to treatment allocation; use of blinded Outcomes Assessors and unblinded Infusion Nurses; and measures to block view of the [REDACTED] and other infusion equipment/supplies throughout the infusion.

All subjects will undergo a screening visit, baseline visit, treatment period, follow-up visits, and an-end-of-study/early-termination visit. Safety and tolerability assessments will occur at every visit. Cognitive and other assessments will be performed at Baseline and periodically during subsequent visits through End of Study/Early Termination.

Objectives: The primary objective of the study is to assess the safety and tolerability of an infusion dosing regimen of GRF6019 in subjects with severe AD. As a secondary objective, the study will assess the potential effects of GRF6019 on cognition and function. The exploratory objectives include serial compositional analysis of plasma proteins to identify specific biomarkers associated with cognitive function and/or indicators of disease progression.

Endpoints: Primary Endpoint(s):

- Incidence of treatment-emergent AEs and SAEs identified by MedDRA preferred term (PT) and grouped by MedDRA System Organ Class (SOC)

Secondary Endpoint(s):

- Changes in safety laboratory parameters
- Changes in vital signs
- Changes in body weight

[figure not shown]
- Changes in physical exam
- Changes in electrocardiogram (ECG) parameters
- Changes in the Mini-Mental Status Examination (MMSE)
- Changes in the Severe Impairment Battery (SIB)
- Changes in the Alzheimer's Disease Cooperative Study Group Activities of Daily Living Inventory for Severe Alzheimer's Disease (ADCS-ADL-Severe)
- Changes in the Alzheimer's Disease Cooperative Study – Clinical Global Impression of Change Caregiver Input (ADCS-CGIC)
- Change on the Neuropsychiatric Inventory (NPI) or NPI Nursing Home Version (NPI-NH)

Exploratory Endpoint(s):

- Proteomic assessment of plasma for investigation of study-related biomarkers

Population:	Approximately 20 subjects between 60 and 95 years of age with severe AD. Assuming a drop-out rate of 20%, enrollment of 20 subjects would yield approximately 16 evaluable subjects.
Phase:	2
Number of Sites:	Up to 4 sites in the United States (US)
Description of Study Agent:	GRF6019: A [REDACTED] human plasma protein fraction for IV infusion.
Study Duration:	Approximately 12 months
Subject Duration:	Approximately 9 weeks

SCHEMATIC OF STUDY DESIGN

1.2 STUDY ORGANIZATION

The name and contact information of the responsible party and individuals involved with the study (e.g., investigator(s), Sponsor's medical expert and study monitor, Sponsor's representative(s), laboratories, steering committees, and oversight committees (including independent ethics committees (IECs) and Institutional Review Boards (IRBs), as applicable) will be maintained by the Sponsor, or their designee, and provided to the investigator.

2 INTRODUCTION

2.1 BACKGROUND INFORMATION

Alzheimer's disease (AD) is a progressive neurodegenerative disease associated with cognitive decline. The initial symptoms typically include an inability to retain recently acquired information, whereas memory for remote events may be spared until late stage disease ([Alzheimer's Association 2018](#)). During the course of the disease, synapses and ultimately neurons are lost in the cerebral cortex, hippocampus, and subcortical structures (including selective cell loss in the nucleus basalis of Meynert), locus coeruleus, and nucleus raphe dorsalis. Imaging studies have found characteristic changes in perfusion and cerebral glucose metabolism (e.g., reduction in the parietal lobe and temporal cortices in early-stage disease, prefrontal cortex in late-stage disease). Neuropathologically, neuritic or senile plaques (composed of neurites, astrocytes, and glial cells around an amyloid core) and neurofibrillary tangles (composed of tau paired helical filaments) are the hallmarks of AD. Some of these pathologic changes (e.g. plaques) precede symptoms of impaired cognition ([Mayeux 2010](#)).

As of 2018, approximately 5.7 million Americans have AD. This number includes an estimated 5.5 million people age 65 and older. By mid-century, that number is expected to grow to 14 million. It is estimated that by 2050, nearly 1 million new cases will be diagnosed per year ([Alzheimer's Association 2018](#)). After being diagnosed with AD, the average life expectancy of a person who is 65 or older is 5.7 years for women and 4.2 years for men, and approximately 1.5-3 years of that time will be spent in the most severe stage of the disease, and this time is commonly spent in a skilled nursing facility ([Larson 2004](#), [Alzheimer's Association 2018](#)).

While approved therapies, including acetylcholinesterase inhibitors (e.g., donepezil) and the N-Methyl-D-aspartic acid (NMDA) receptor agonist memantine, ameliorate symptoms, the magnitude of this symptomatic effect is moderate. Moreover, these drugs do not slow the progression of the disease ([Alzheimer's Association 2018](#)). Given the increasing prevalence and socioeconomic impact of the disease, identifying treatments for maintaining or improving cognitive function is an area of substantial unmet medical need.

In 2011, data from heterochronic parabiosis in mice suggested that increased levels of systemic chemokines and increased immune signaling molecules may affect the aging brain, and that rejuvenating factors from young animals may ameliorate the effects of aging ([Villeda 2011](#)). Following their initial findings, studies were designed to explore the therapeutic effects of systemic exposure of aged mice to young plasma by direct injection ([Villeda 2014](#)). Systemic administration of young plasma in aged mice improved age-related cognitive impairments. In addition, the data demonstrated that exposure of old mice to young plasma counteracts age-related impairment at the molecular and structural levels in the hippocampus ([Villeda 2014](#)). These studies lay the foundation for the hypothesis that soluble circulating factors from young plasma may have beneficial effects on human cognition.

Results from nonclinical studies conducted at Alkahest (see Section 2.2, “Rationale” below) suggest there is a beneficial effect of [REDACTED] human plasma and plasma protein fraction in age-related cognitive decline and histopathological endpoints in mouse models. These studies have raised the intriguing possibility that there are factors present in human plasma that may prove beneficial against brain aging and ameliorate some of the age-associated memory impairments in people, especially in those experiencing rapid cognitive decline from age-associated neurodegenerative diseases.

2.2 RATIONALE

Study ALK6019-202 will evaluate the safety and tolerability of administering GRF6019 via IV infusions in subjects with severe AD. GRF6019 has been manufactured specifically for investigational purposes. It is a purified [REDACTED] plasma protein fraction made from pooled human plasma [REDACTED]

The rationale for using a plasma protein fraction was based on several factors. Although plasma is widely used, there are inherent risks such as the potential transfer of unknown pathogens to recipients, histoincompatibility, and allergic reactions to proteins such as clotting factors and immunoglobulins. Therefore, the Blood Products Industry has developed safer products based on pooling plasma from multiple donations, fractionating them into more defined products, and adding additional processing steps to reduce the potential for pathogen transmission. Leveraging this fractionation technology, GRF6019 is a [REDACTED]

Nonclinical studies conducted at Alkahest have demonstrated that both young whole plasma and [REDACTED] plasma protein fraction confer beneficial outcomes in age-related cognitive decline and histopathological endpoints in mouse models [REDACTED]

Our nonclinical studies were initiated to test whether the positive effects observed with young mouse plasma could be replicated using [REDACTED] human plasma. Treatment of aged NODscid (non-obese diabetic severe combined immunodeficiency) mice with [REDACTED] human plasma (100-150 μ L per injection, two injections per week for 3-5 weeks) resulted in improved cognitive and motor performance in standard behavioral tests. These cognitive changes were further supported by electrophysiological and histological correlates of enhanced memory. Together, these results provided support for the hypothesis that [REDACTED] plasma infusions may have functional benefits to man, potentially ameliorating or halting the progression of cognitive decline associated with AD [REDACTED].

We evaluated the effects of both [REDACTED] plasma and plasma protein fraction using various dosing paradigms in NODscid, NSG (NODscid Gamma) and C57BL/6J mice. Initially, mice were dosed with 150 μ L of [REDACTED] plasma, [REDACTED] plasma protein fraction or saline (control) via IV infusions 2 times per week for 5 weeks [REDACTED]. A subsequent study examined the same dosing regimen for a period of 23 weeks, to assess the effects of treatment on age-dependent changes in behavioral and cognitive function over a period of approximately 6 months [REDACTED]. Following these early studies, we elected to assess a novel dosing regimen of 150 μ L for 7 consecutive days (referred to as “pulsed dosing”), both alone and compared to other intermittent weekly dosing regimens [REDACTED]. Our final study examined pulsed dosing of 150 μ L for 5 consecutive days [REDACTED], which is the pulse-dosing regimen chosen for ALK6019-202.

Based on our non-clinical studies, we observed significant improvements in cognitive performance and histological correlates with a [REDACTED] plasma protein fraction. In addition, studies with [REDACTED] plasma protein fractions demonstrated that the beneficial effect continued long after initial dosing, indicating there is not a requirement for continuous repeat dosing. The effects were long-lived but did diminish over time such that 3 months after dosing benefits just reached significance.

Together, these studies indicate that 5 consecutive days of dosing (“pulsed dosing”) of GRF6019, [REDACTED] [REDACTED]. If safety and efficacy are demonstrated with GRF6019, pulsed dosing may be more convenient than weekly or monthly dosing for patients.

Severe AD patients will be selected for inclusion in this clinical study as they have marked deficits in cognitive function and suffer from a disease with limited treatment options, making them a population for whom the balance of risk to potential benefit of treatment with GRF6019 is favorable.

[figure not shown]
A randomized, placebo-controlled, double-blind study design has been selected to reduce or eliminate bias while facilitating the identification of a safe and feasible dosing paradigm, trends in changes of cognitive endpoints, and potential plasma derived factors that may affect these parameters. A 2:1 randomization ratio will increase the number of subjects exposed to active GRF6019 and thus provide additional safety data. Within-subject and between-group cognitive changes associated with the use of GRF6019 will be evaluated.

Thus, while the primary objective of this study is safety and tolerability, and the study does not have the statistical power to test specific hypotheses regarding changes in cognitive function, the results are nevertheless expected to lay the foundation for larger trials designed and powered to characterize the potential benefits of GRF6019 in severe AD and other neurodegenerative disorders typified by cognitive dysfunction.

Human dose levels were selected based on known safety through clinical experience and scaling from efficacy in nonclinical studies. No safety concerns were observed in nonclinical studies using repeated doses of 150 μ L in mice.

GRF6019 is a complex mixture consisting of multiple proteins [REDACTED] and is dosed by infusion of specified volumes, thus, using allometric scaling, a dose of 150 μ L yields an equivalent human dose using body surface area scaling of 28.4 mL. Allometric scaling is used for small molecules whose elimination is dependent on hepatic metabolism. Alternative scaling methods include mg/kg (recommended for macromolecules >100 kDa) and volumetric scaling based on relative blood volumes. Because GRF6019 contains a complex mixture of proteins with a molecular weight predominantly <100 kDa, and because the beneficial effects of these proteins on cognition are believed to occur in the circulation, the concentration of these proteins per blood volume may be the scaling method most likely to accurately estimate the human potential effective dose.

Using isometric scaling based on blood volume, the mouse dose of 150 μ L is equivalent to a human dose of 413 mL, as outlined in [Table 1](#). The dose used in this study is 250 mL GRF6019, which is below the equivalent human dose of 413 mL.

2.3 POTENTIAL RISKS AND BENEFITS

2.3.1 KNOWN POTENTIAL RISKS

Collected human plasma may be used as a therapeutic product (known as “plasma” or “fresh frozen plasma”) or as source material for the production of pharmaceutical fractionated products (known as “plasma products” or “plasma derivatives”) (Burnouf 2007). GRF6019, a [REDACTED] human plasma protein fraction, [REDACTED] serves as a viable source of soluble, infusible plasma proteins from [REDACTED] healthy donors. [REDACTED]

[REDACTED] ABO antigen typing is not required prior to administration. Finally, the additional steps taken during production to remove viral pathogens provide an increased margin of pathogen safety in comparison to fresh frozen plasma.

[REDACTED] GRF6019 is not expected to significantly alter the urinalyses of recipients, their bleeding times, coagulation times, prothrombin times, prothrombin consumption, platelet counts or fibrinogen levels when given in quantities of up to 1000 mL. Decreased blood pressure may occur, particularly following rapid infusion. The blood pressure may normalize spontaneously after the slowing or discontinuation of the infusion. [REDACTED]

GRF6019 is made from human plasma and may carry a risk of transmitting infectious agents, e.g., viruses, the variant Creutzfeldt-Jakob disease (vCJD) agent, and, theoretically, the Creutzfeldt-Jakob disease (CJD) agent. The risk that GRF6019 can transmit an infectious agent has been reduced by screening plasma donors for prior exposure, testing donated plasma, and including manufacturing steps with the capacity to inactivate and/or remove pathogens.

2.3.2 KNOWN POTENTIAL BENEFITS

There is no known reported benefit of administering GRF6019 to patients with severe AD.

3 OBJECTIVES AND PURPOSE

The primary objective of this study is to assess the safety and tolerability of GRF6019, a [REDACTED] human plasma protein fraction administered by IV infusion in subjects with severe AD. Secondarily, this study aims to assess the effects of GRF6019 on subjects’ cognition and function. As an exploratory objective, blood and plasma will be collected and analyzed to identify specific biomarkers associated with cognitive functional changes and/or indicators of AD progression.

4 STUDY DESIGN AND ENDPOINTS

4.1 DESCRIPTION OF THE STUDY DESIGN

This will be a prospective, randomized, double-blind, placebo-controlled study conducted at up to four (4) sites in the United States.

During the Screening Period, subjects will undergo all Screening assessments including an echocardiogram. During the Baseline Period, subjects and their caregivers will complete a series of cognitive and functional assessments.

Subjects that meet eligibility for inclusion in the trial will be randomized in a 2:1 ratio to GRF6019 (Group 1) or placebo (Group 2). Treatment groups will be stratified by sex. There will be one (1) dosing period during which subjects randomized to GRF6019 will receive GRF6019, while subjects randomized to placebo will receive placebo. The dosing period consists of 5 consecutive days (“pulsed dosing”) of IV infusions of 250 mL of either GRF6019 or placebo.

During the 5-day dosing period, subjects who do not already reside in a long-term care/skilled nursing facility will be admitted to such a facility to facilitate safety evaluation. Safety and tolerability assessments will occur at every visit. Cognitive and functional assessments will be performed at Baseline and periodically at subsequent visits through End of Study/Early Termination. In the event of early termination of a subject who has received at least one dose, the End of Study procedures will be performed unless the subject/subject’s legally authorized representative has withdrawn consent. A comprehensive safety and efficacy assessment of all data *in toto* will be conducted at the end of the study.

The overall duration of the study is approximately 12 months from study initiation (i.e., first subject enrolled) to study completion (i.e., last subject last visit). The recruitment period is expected to be approximately 9 months. The subject participation period is 9 weeks from Screening through End of Study, unless prematurely discontinued.

4.2 STUDY ENDPOINTS

4.2.1 PRIMARY ENDPOINTS

The primary endpoints pertain to safety and tolerability of the GRF6019 dosing regimen in subjects with severe AD.

The primary safety endpoint is as follows:

- Incidence of treatment-emergent adverse events (AEs) and serious adverse events (SAEs) identified by MedDRA PT and grouped by MedDRA SOC.

Tolerability endpoint is as follows:

- Number of subjects completing 4 weeks after receiving at least 5 infusions.

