5.4.2 HANDLING OF PARTICPANT WITHDRAWALS OR TERMINATION

Subjects will be encouraged to complete the study and all assessments. However, subjects may voluntarily withdraw at any time, and the investigator may discontinue individual subjects from the study at any time.

Approximately 20 subjects will be enrolled in the study with the intent of obtaining ~16 evaluable subjects who have received at least 5 doses and completed through Visit 8. Subjects who discontinue or are unblinded prior to completing Visit 8 may be replaced. Subjects who withdraw or are withdrawn during Screening will be replaced.

Subjects who have received at least one infusion but are withdrawn or withdraw from the study will be encouraged to complete the End of Study procedures within approximately 4 weeks of their last visit. For post-study AE and SAE reporting, see [Section 8.3.1](#). The primary reason for study discontinuation will be documented on the case report form (CRF).

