7.3 STUDY SCHEDULE

Visit windows (when noted) should be benchmarked relative to Visit 3 for a subject, such that subjects complete the entire study by Day 33 ± 7 days. Study visit procedures are listed in the recommended order in which they should be completed.

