7.3.4 TREATMENT

The treatment period includes a total of 5 infusions during Week 1. It is anticipated that sites will infuse subjects with 5 doses over 5 days. A “grace day” is allowed in the event of unanticipated safety or health concerns during the treatment period.

Visits 3 -7 (Days 1-5)

- Perform the following procedures prior to administering study treatment:
 - Review AEs and concomitant medications.
 - Obtain samples for proteomics/epigenetics/biobanking; fasting samples preferred (**Visit 3 Only**).
 - Obtain sample for ApoE genotype testing (**Visit 3 Only**).
 - Obtain pre-infusion safety laboratory samples and assess results **prior to the next day's infusion (Visits 4, 5, and 6 Only)**. (When using an i-STAT Handheld Blood Analyzer, the blood sample(s) may be obtained on the same day as the infusion, provided that all pre-infusion safety lab results are available and interpreted prior to the subject's infusion start on Visits 5, 6, and 7.)
 - Collect urine for urinalysis (**Visit 6 Only**).
 - Measure and record the subject's weight in kilograms.
 - Perform targeted physical exam (i.e. auscultation of heart and lungs and assessment of peripheral edema) (**Visits 3, 5, and 7 Only**).
 - Perform 12-lead ECG (**Visits 3 and 5 Only**).
 - Collect pre-infusion vital signs.
- Administer study treatment and perform safety assessments per the Infusion Administration Manual.

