 1. SIB
 2. ADCS-CGIC

Follow-up Visit 9 (Day 12 ± 3 days)

- Review AEs and concomitant medications.
- Collect the following:
 - Vital signs and subject's weight in kilograms.
 - Blood samples for safety labs (fasting samples preferred).
- Ensure the subject has had an opportunity to eat a meal or snack prior to administering cognitive and functional assessments.
- Administer cognitive and functional assessments in the following order:

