7.3.6 FINAL STUDY VISIT

Visit 10, End of Study (Day 33 ± 7 days)

- Review AEs and concomitant medications.
- Collect the following:
 - Vital signs and subject's weight in kilograms.
 - Blood and urine samples for exit safety labs (fasting samples preferred).
 - Samples for proteomics/epigenetics/biobanking (fasting samples preferred).
- Perform the physical exam.
- Perform the 12-lead ECG.
- Ensure the subject has had an opportunity to eat a meal prior to administering the cognitive and functional assessments.
- Administer cognitive and functional assessments in the following order:

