15 SCHEDULE OF EVENTS

15.1 SCHEDULE OF EVENTS TABLE

	Screening ^a / Baseline Visit		Treatment					Follow-up		End of Study/ Early Termination Visit
	1	2	3	4	5	6	7	8	9	
Visit	1	2	3	4	5	6	7	8	9	10
Infusion Number			1	2	3	4	5			
Day	Day -28 to -8	Day -7 to -1	1	2	3	4	5	6 + 1-3 days ^b	12 ± 3 days	33 ± 7 days
Week							1		2	5
Informed Consent	X									
Medical History	X									
Demographics	X									
Vital Signs (BP, HR, temp, RR)	X	X	X ¹	X	X	X				
12-lead ECG	X		X ¹		X ¹			X		X
MHIS	X									
Echocardiogram	X									
Physical Exam	X									X
Height	X									
Weight	X		X ¹	X	X	X				
Targeted Physical Exam			X ¹		X ¹		X ¹			
Concomitant Medication	X	X	X ¹	X	X	X				
Adverse Event Review	X ^a	X	X ¹	X	X	X				
Drug Administration										
Randomization			X ¹							
GRF6019/Placebo Infusion			X	X	X	X	X			
Labs										
Screening Lab Panel ^c	X									
Urinalysis ^d	X				X ¹			X		X
ApoE Genotype Testing			X ¹							
Proteomics/epigenetics/biobanking			X ¹					X		X
Pre-infusion Safety Labs ^e				X ¹	X ¹	X ¹				
Follow-up Safety Labs ^f								X	X	
Exit Lab Panel ^g										X
Cognitive and Functional Assessments										
MMSE	X							X		X
Severe Impairment Battery		X						X	X	X
ADCS-ADL-severe		X								X
ADCS-CGIC		X						X	X	X
NPI or NPI-NH ^h		X						X		X

Notes:	X ¹ : To be performed prior to infusion start. During, and for 2 hours after, each infusion, vital signs should be collected according to the schedule outlined in the Infusion Administration Manual.
	a: Screening visit may be split to allow for sufficient time to complete all procedures. AEs and concomitant medications should be recorded during split visits, if applicable.
	b: The treatment window is 5 days. Visit 8 may occur on Day 6 + 1 to 3 days following treatment to potentially avoid a weekend visit, if needed. The preference for Visit 8 is for the subject to be seen on Day 6.

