4.8 Tolerability

Number of subjects completing 4 weeks after receiving at least 5 infusions will be tabulated (Table 14.1.9).

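### Does the tolerability count need a written rule tying its 4 weeks to Visit 10?

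*Protocol*

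**What the plan says.** Protocol 4.2.1 places the tolerability endpoint under the primary endpoints: "Number of subjects completing 4 weeks after receiving at least 5 infusions". SAP 4.8 carries it over: "Number of subjects completing 4 weeks after receiving at least 5 infusions will be tabulated (Table 14.1.9"). No start date, end date or completion rule is attached in either place.

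The timing comes from the schedule:

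- **Infusions.** Protocol 7.3.4 puts the five infusions on Days 1 to 5. A grace day "is allowed in the event of unanticipated safety or health concerns during the treatment period", and SAP 4.6 confirms that the fifth infusion may then fall on the sixth day.
- **End of study.** Protocol 7.3 has visit windows "benchmarked relative to Visit 3 for a subject, such that subjects complete the entire study by Day 33 ± 7 days". The last visit, in Protocol 7.3.6, is "Visit 10, End of Study (Day 33 ± 7 days").
- **Withdrawals.** Under Protocol 5.4.2, subjects who leave after at least one infusion "will be encouraged to complete the End of Study procedures within approximately 4 weeks of their last visit". The schedule in Protocol 15.1 has one column for both cases, headed "End of Study/ Early Termination Visit".

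**The concern.** Two programmers could read the endpoint differently. One might count subjects who attended Visit 10. The other might count subjects with 28 or more days between infusion 5 and their last visit.

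The second reading can err in two directions. Visit 10 may be held a week before its nominal day, so a subject who took every infusion and finished the study in window could be counted as not tolerating treatment. A subject who withdrew after infusion 5 and came back late for the termination procedures could be counted as a success. The shared column in the schedule suggests that attendance alone would not separate these cases.

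This would matter because tolerability is part of the primary objective and this is the only endpoint carrying that name. The arms are also small, so one reclassified subject moves a percentage visibly.

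**Working it through.** **Inputs.** Infusion 5 on Day 5, or Day 6 with a grace day (Protocol 7.3.4, SAP 4.6). Visit 10 on Day 33 ± 7, counted from Visit 3 (Protocol 7.3, 7.3.6). Visit 8 on Days 6 to 9 and Visit 9, "Follow-up Visit 9 (Day 12 ± 3 days"), on Days 9 to 15 (Protocol 7.3.5). Termination procedures up to about 28 days after the last visit (Protocol 5.4.2).

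**The plan's own figure.** Infusion 5 plus 4 weeks is 5 + 28 = Day 33. This equals the nominal day of Visit 10, and no other visit lies near it: Visit 9 ends by Day 15.

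**Reading A: 28 elapsed days.** The window runs from 33 − 7 = Day 26 to 33 + 7 = Day 40, which is 15 days. Elapsed days = visit day − day of infusion 5, and a subject fails if this is below 28.

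| Clock | Elapsed days over the window | Window days that fail |
|---|---|---|
| Infusion 5 on Day 5 | 26 − 5 = 21 to 40 − 5 = 35 | Days 26–32, 7 of 15 (46.7%) |
| Infusion 5 on Day 6 (grace day) | 26 − 6 = 20 to 40 − 6 = 34 | Days 26–33, 8 of 15 (53.3%) |
| From Day 5, counting Day 5 itself | 22 to 36 | Days 26–31, 6 of 15 (40%) |
| From first infusion, Day 1 | 25 to 39 | Days 26–28, 3 of 15 (20%) |

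These are shares of calendar days, not of subjects. The documents give no distribution of visit dates.

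For a subject who withdrew after infusion 5 on Day 5, the latest termination visit is the last visit + 28:

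- Last visit Visit 7: 5 + 28 = Day 33, which is 28 days after infusion 5.
- Last visit Visit 8: Days 34 to 37, which is 29 to 32 days.
- Last visit Visit 9: Days 37 to 43, which is 32 to 38 days.

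Each can reach 28 days, but after Visit 7 only at the very end of an approximate limit.

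**Reading B: all 5 infusions and study completed through Visit 10.** Every day from 26 to 40 counts, so 0 of 15 fail, and no early terminator is counted.

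**Which reading the documents support.**

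- Protocol 7.3 treats the whole range of Day 33 ± 7 as completing the study.
- SAP 5.1 to 5.5 and 6.4 label the results of that visit as Day 33, whatever the actual day in the window. SAP 4.9 likewise counts visits by scheduled timepoint.
- SAP 4.1 reports subjects who completed the study apart from those who finished dosing and then left.
- SAP 5 has its own rule for results from early termination visits, so the data must already identify them. Protocol 5.4.2 also has the reason for discontinuation recorded on the case report form.

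**Size of one reclassification.** 20 subjects at 2:1 is 20 × 2/3 = 13.3 and 20 × 1/3 = 6.7, about 13 and 7. One subject is 1/13 = 7.7 percentage points on GRF6019 or 1/7 = 14.3 points on placebo. This holds for any reclassified subject and says nothing about how many there would be.

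**The case for a change.** The strongest case for acting is that probable intent is not a derivation. Elsewhere the protocol names a visit when it means one: Visit 8 for the evaluable target in 5.4.2 and for body weight in 4.2.2. The SAP writes out formulas for relative day, age, exposure and treatment completion, and a rule for termination visits in the efficacy tables. The tolerability count has nothing comparable. Under the elapsed-day reading a grace day even fails a subject seen exactly on Day 33 (33 − 6 = 27 days). Grace days are given for safety or health concerns, so the artefact would fall on those subjects. The remedy would cost one sentence.

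The missing sentence stands as a fact, and the arithmetic is right. The predicted harm does not follow from it, because both errors need a programmer to adopt a reading that the schedule, the nominal-day labels and the disposition categories all speak against. Calling the early terminator's pass an error also presupposes that completion through Visit 10 is the right definition, which concedes the point. On a literal 28-day endpoint, that subject would have met it.

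SAP 1 also places the table shells in a separate working document, where a derivation for Table 14.1.9 would normally sit. Its absence from SAP 4.8 does not show that none exists.

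**Conclusion.** The concern identifies a missing detail in a descriptive count, not a fault in the plan. Analysts can fill it sensibly from the documents as they stand: all 5 infusions received, and the study completed through Visit 10.

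The consequence is small. No hypothesis test, error rate or sample size depends on the count. Protocol 10.4.2 evaluates safety and tolerability through adverse events and those leading to discontinuation, and the Protocol Summary lists only adverse event incidence as primary. SAP 11 provides listings of tolerability, study visits, exposure and disposition, so with about 20 subjects any reader of the report can rebuild the count under either reading. Amending the protocol for this would need ethics board approval (Protocol 12.2) and would gain nothing.

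This rests on two assumptions: that the analyst follows the SAP's nominal-visit convention, and that completion status is taken from the disposition data rather than from attendance in the shared schedule column. If both hold, no subject is misclassified. If the elapsed-day reading were used instead, the number affected cannot be estimated from the documents. It would be zero if every completer were seen at least 28 days after infusion 5 and no early terminator had a termination visit that late.
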